2.3 RISK/BENEFIT ASSESSMENT

2.3.1 KNOWN POTENTIAL RISKS

The risks associated with ketamine have been observed in studies evaluating its use for general anesthesia (as a sole agent, for induction, or as a supplement to other agents), which generally involve higher doses than those to be used in this study.⁴⁶

Immediate risk of ketamine use may include

- Hypertension and tachycardia – These are common events at higher doses. Ketamine is contraindicated in patients for whom a significant elevation of blood pressure would constitute a serious hazard. (Of note, the low doses to be used in this study have not previously been associated with clinically significant changes in blood pressure or heart rate.³⁶)
- Psychotomimetic effects – These have occurred in approximately 12% of patients following anesthetic doses. These may range from pleasant dream-like states to vivid imagery, hallucinations, and emergence delirium.
- Respiratory depression – This is an uncommon event and may occur with overdosage or too rapid a rate of administration.
- Nystagmus, diplopia – These are common events. Rarely these may be associated with increases in intraocular pressure.
- Enhanced skeletal muscle tone
- Anorexia, nausea, vomiting
- Anaphylaxis

Long-range risks of ketamine include

- Pediatric neurotoxicity - Animal studies demonstrate increased neuronal apoptosis in developing juvenile brains and long-term cognitive deficits when used for longer than 3 hours.

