6.3 MEASURES TO MINIMIZE BIAS: RANDOMIZATION AND BLINDING

Randomization will occur postoperatively at the time of study medication preparation. Patients will be randomized in a 1:1 ratio to ketamine or normal saline placebo. Randomization will occur in blocks of 4. The randomization scheme will be held by the Investigational Drug Service.

Patients, research team members, and clinical staff (nurses, physicians) will be blinded to treatment allocation. To facilitate blinding, study medication for both the ketamine group and the control group will be delivered in 100 mL bags with identical appearance except for a unique study identifier.

Intentional unblinding of the clinical staff may occur in the case of serious adverse events if the attending physician feels knowledge of the treatment allocation will impact clinical decision making. The principal investigator will be notified of all instances of intentional unblinding.

Inadvertent unblinding may occur if the patient experiences side effects such as nystagmus, hallucinations, sedation, or hypertension/tachycardia. To detect inadvertent unblinding of the patient, we will ask the patient during the final study visit if they believe they received ketamine or placebo. To minimize the effects of inadvertent unblinding on study results, endpoints will be measured by study staff who were not present during the study medication infusion.

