8.2 SAFETY AND OTHER ASSESSMENTS

Psychotomimetic Side Effects

Psychotomimetic effects will be quantified using the Brief Psychiatric Rating Scale (BPRS) four-item positive symptom subscale^{36,54} and using the modified 6-item Clinical Administered Dissociative State Scale (CADSS-6).⁵⁵ The BPRS four-item subscale yields a score between 4 (no symptoms) and 28 (extremely severe). The CADSS-6 yields a score between 0 (no symptoms) and 24 (severe symptoms). Both scales will be administered by a research team member midway through the study medication infusion (approximately 1-2 hours after the start of the bolus loading dose).

Clinical and Adverse Events Checklist

Additional side effects of ketamine will be detected using the Clinical and Adverse Events Checklist.⁵⁶ This checklist will be administered by a research team member midway through the study medication infusion (approximately 1-2 hours after the start of the bolus loading dose). The checklist will be repeated on post-infusion day 14 to monitor for resolution of any side effects.

Level of Sedation

Although the doses of ketamine used in this study are not expected to produce clinically significant sedation, patients will be monitored for sedation using the Richmond Agitation and Sedation Scale (RASS). RASS assessments will be conducted by the clinical bedside nurse per standard nursing protocols of the ICU. The nurse will also be asked to perform one extra RASS assessment at the end of the 10-minute bolus loading dose. If the RASS score is ever -2 or lower, the study medication will be held according to the protocol described in section 7.1.

Vital Signs during Study Medication Infusion

During the infusion, participants will receive vital sign monitoring per intensive care unit standard of care. This will include continuous telemetry, continuous pulse oximetry, and either intermittent

noninvasive blood pressure (at least hourly) or continuous invasive blood pressure (if an arterial catheter is present). Vital signs will be documented in the electronic health record by the clinical bedside nurse per unit standard of care. The research team will retrieve vital signs from the electronic health record.

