Safety events will include significant hypertension during the infusion, defined as systolic blood pressure > 180 mmHg or the administration of an antihypertensive medication that is not one of the patient's home medications. Another safety event will be tachycardia, defined as heart rate > 100 beats per minute, during the infusion.

Nausea and Vomiting

At each post-infusion study visit, participants will be asked if they have experienced nausea or vomiting in the past 24 hours. If present, the patient will be asked to classify the event as mild, moderate, or severe. In addition, the electronic medical record will be reviewed for administration of antiemetic medication.

Baseline Factors Potentially Related to Depression

At the time of enrollment, the patient will complete several surveys evaluating factors that may be related to their depressive history or that may predict treatment responsiveness. These surveys will include the Generalized Anxiety Disorder 7-item scale (GAD-7),⁵⁷ the Alcohol Use Disorders Identification Test (AUDIT),⁵⁸ the Drug Abuse Screening Test (DAST-10),⁵⁹ and the Childhood Trauma Questionnaire (CTQ).⁶⁰

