9.2 SAMPLE SIZE DETERMINATION

The sample size of 32 has been selected to allow the primary descriptive endpoints to be measured with acceptable levels of precision:

- Primary Endpoint 1: Fraction of approached patients who enroll in the trial

- Conservatively assuming that 25% of approached patients will enroll, then $n = 32$ patients will allow this proportion to be measured with a 95% confidence interval width of $\pm 15\%$:

$$95\%CI = \pm 1.96 \sqrt{\frac{p(1-p)}{n}} = \pm 1.96 \sqrt{\frac{(0.25)(0.75)}{32}} = \pm 0.15$$

- Primary Endpoint 2: Fraction of planned study medication infusions that are completed
 - If we assume that 90% of planned infusions are completed, then $n = 32$ patients will allow this proportion to be measured with a 95% confidence interval width of $\pm 10\%$:

$$95\%CI = \pm 1.96 \sqrt{\frac{p(1-p)}{n}} = \pm 1.96 \sqrt{\frac{(0.90)(0.10)}{32}} = \pm 0.10$$

- Primary Endpoint 3: Fraction of participants with MADRS scores available at all specified time points
 - If we assume that 95% of participants will have scores available at all specified time points, then $n = 32$ patients will allow this proportion to be measured with a 95% confidence interval width of $\pm 7\%$:

$$95\%CI = \pm 1.96 \sqrt{\frac{p(1-p)}{n}} = \pm 1.96 \sqrt{\frac{(0.95)(0.05)}{32}} = \pm 0.07$$

This sample size does not provide power to test the secondary endpoints for superiority. However, the observed values will be used to determine effect sizes, as well as standard deviations for the observed values. These quantities will inform the sample size calculation for the full-scale clinical trial. A minimum of 24-30 patients has previously been recommended for estimating effects sizes,^{61,62} so this feasibility trial should be large enough to provide the necessary estimates.

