9.4 STATISTICAL ANALYSES

9.4.1 GENERAL APPROACH

For descriptive statistics, categorical data will be presented using frequency counts and percentages, normally distributed continuous data will be presented using means and standard deviations, and non-normally distributed continuous data will be presented using medians and interquartile ranges.

Normality will be assessed using visual analysis of histograms and using the Kolmogorov-Smirnov test. All inferential tests will be two-tailed, and p-values < 0.05 will be considered statistically significant.

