9.4.4 SAFETY ANALYSES

Psychotomimetic Symptoms:

The BPRS four-item positive symptom subscale score and the CADSS-6 score will be calculated for each patient. The distribution of scores will be assessed for normality using visual analysis of histograms and using the Kolmogorov-Smirnov test. If the scores are normally distributed, then the mean score in the two groups will be compared using a two-sample t-test. If the scores are not normally distributed, then the median score in the two groups will be compared using a Wilcoxon rank sum test.

Clinical and Adverse Events Checklist:

The number of patients reporting each side effect during the study medication infusion will be determined. The incidence of each side effect will be compared between the two groups using a chi-square test (or using a Fisher exact test in the case of rare side effects).

Significant Hypertension during Infusion:

The number of patients experiencing a systolic blood pressure > 180 mmHg during the study medication infusion or receiving an antihypertensive medication during the infusion that is not on the patient's home medication list will be determined. The incidence of significant hypertension will be compared between the two groups using a chi-square test.

Tachycardia during Infusion:

The number of patients experiencing a heart rate > 100 beats per minute during the study medication infusion will be determined. The incidence of tachycardia will be compared between the two groups using a chi-square test.

Nausea and Vomiting:

The number of patients reporting nausea and vomiting will be determined. The incidence of nausea and vomiting will be compared between the two groups using a chi-square test.

Other adverse events will be coded and reported as described in section 8.3.

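### Section 9.4.4 compares blood pressure between arms only as a yes/no composite, so the plan gives no estimate in mmHg of ketamine's effect, although the readings are already retrieved

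*Combined protocol and SAP*

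**What the plan says.** Section 8.2 provides for continuous arterial pressure where there is a catheter, and otherwise cuff readings at least every hour. It adds: "The research team will retrieve vital signs from the electronic health record". It then sets the safety event: "Safety events will include significant hypertension during the infusion, defined as systolic blood pressure > 180 mmHg", or a new antihypertensive that is not one of the patient's home medications.

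Section 9.4.4 turns this into the only between-arm blood pressure analysis: "The number of patients experiencing a systolic blood pressure > 180 mmHg during the study medication infusion", or receiving such an antihypertensive, with incidence compared by chi-square. No summary of the pressures themselves, no effect estimate and no confidence interval is specified. In the same section, the psychotomimetic scales (BPRS subscale and CADSS-6) are compared as scores, by mean or median.

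Section 2.3.1 puts hypertension and tachycardia at the head of the immediate risks and adds that "the low doses to be used in this study have not previously been associated with clinically significant changes in blood pressure or heart rate". Section 10.1.6 has the independent safety monitor review vital signs every six months, without naming a summary.

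On size, section 9.2 says "The sample size of 32 has been selected to allow the primary descriptive endpoints to be measured with acceptable levels of precision". It disclaims power for the efficacy comparisons ("This sample size does not provide power to test the secondary endpoints for superiority") and is silent on safety comparisons.

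**The concern.** A repeated numeric measurement is reduced to one yes/no item per patient. Most patients whose pressure rises by, say, 8 to 16 mmHg would stay below 180 mmHg and untreated, and would count the same as patients with no rise. With about 16 per arm, the comparison will usually rest on a handful of events. A non-significant chi-square would then say little about whether, or by how much, this load plus infusion raises pressure.

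What is lost is an estimate. The reassurance in section 2.3.1 rests on a pilot of a 96-hour infusion whose title in the reference list says clonidine was co-administered. Section 2.2 says the longer infusion has not been tested around the time of surgery. This trial collects readings that bear directly on that statement in surgical patients, and the plan does not use them.

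**Working it through.** **The plan's own figure.** None exists for blood pressure. The sample-size basis in 9.2 is precision of proportions, and its first figure reproduces: 1.96 × √(0.25 × 0.75 / 32) = 0.150, stated as ±0.15.

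**Inputs from the documents.** N = 32 (9.2). Allocation: "Patients will be randomized in a 1:1 ratio to ketamine or normal saline placebo" (6.3), so about 16 per arm. Testing level: "All inferential tests will be two-tailed, and p-values < 0.05 will be considered statistically significant" (9.4.1). Infusion of about 3 hours (6.1.2). Composite event and chi-square (9.4.4).

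**Assumed inputs, none in the documents.** Mean systolic pressure 132 mmHg; between-patient/within-patient SD 15/10, 18/12 or 20/15; four infusion readings; 30% to 70% chance of treatment after a reading above 160, lowering later readings by 15 mmHg; one pre-infusion reading, with or without extra noise; true rise 8, 12 or 16 mmHg.

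**Step 1: precision of the adjusted mean, before treatment effects.** With between-patient SD b and within-patient SD w, the mean of four readings has variance b² + w²/4. Adjusting for one pre-infusion reading removes b⁴/(b² + w²). The standard error of the arm difference is √(residual variance × 2/16).

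- SD 15/10: 225 + 25 − 225²/325 = 94.2; SE = √(94.2 × 0.125) = 3.43 mmHg.
- SD 20/15: 400 + 56.25 − 400²/625 = 200.25; SE = √(200.25 × 0.125) = 5.00 mmHg.
- SD 20/15 with a noisier pre-infusion reading (correlation 0.6 instead of 0.75): 456.25 × (1 − 0.36) = 292; SE = √(292 × 0.125) = 6.04 mmHg.

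Multiplying by t(0.975, 29 df) = 2.045, the 95% CI half-width is about 7 to 12 mmHg. By the noncentral t, power in these three cases is 62%, 34% and 25% for an 8 mmHg rise, and over 99%, 87% and 73% for 16 mmHg.

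**Step 2: both analyses simulated, with treatment included.** Uncorrected chi-square on the full composite against regression of mean systolic pressure on arm and pre-infusion pressure:

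| True rise | Composite, chi-square | Adjusted mean |
|---|---|---|
| 8 mmHg | 6-15% | 25-57% |
| 12 mmHg (no extra noise in the pre-infusion reading) | 16-28% | 59-90% |
| 16 mmHg | 28-50% | 71-99% |

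The adjusted mean has more power in every scenario. The smallest gain is about 12 points, with the noisier pre-infusion reading. Its type I error stays near 5%. Treatment shrinks the estimated difference by about 5-15%. The standard error is about 3-6 mmHg, in line with step 1.

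**Step 3: a separate check with one peak value per patient.** Control mean peak 150, SD 20, and 30% of patients peaking above 160 given a new antihypertensive. Composite power comes from exact enumeration of all 16 v 16 tables.

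| Shift | Composite rates | Chi-square power | t-test | Adjusted (r = 0.6) |
|---|---|---|---|---|
| 10 mmHg | 14% v 26% | 14% | 28% | 40% |
| 15 mmHg | 14% v 34% | 28% | 54% | 73% |
| 20 mmHg | 14% v 42% | 47% | 78% | 93% |

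At a 10 mmHg shift the expected counts are 0.14 × 16 = 2.2 and 0.26 × 16 = 4.2 events. For 80% power, the chi-square needs a 5% control rate to rise to about 44%, or a 10% rate to about 53%.

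**The case against.** Four points can be made for the plan.

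- **The event is wider than the cut at 180 mmHg.** A reader might infer that only pressures above 180 can register. That is wrong: 8.2 and 9.4.4 also count any new non-home antihypertensive, so a treated rise counts at any pressure. This stands. The antihypertensive component is in the calculations, and the direction is unchanged.
- **Small numbers, not only the coding, cause the low power.** A reader might infer that a moderate rise is missed because of the yes/no analysis. The documents do not support that: this is a feasibility trial of 32, no safety comparison was sized, and the adjusted mean itself misses an 8 mmHg rise in roughly 43-75% of trials. This also stands, and it is why the case rests on estimation more than on power.
- **The importance is not stated.** No section treats 8 to 16 mmHg as a safety concern, and 9.2 names only the secondary endpoints as informing the full-scale trial. Section 2.3.1 reports no previous association with clinically significant changes; it does not say the doses cannot raise pressure. The clinical concern in 2.3.3 and 5.2 is a significant elevation, which the composite addresses. All fair, and reasons to keep the composite.
- **The size could still be found.** The readings are retrieved, the safety monitor reviews vital signs, and de-identified data will be archived. So it would be too strong to say the effect could never be estimated. What is missing is a pre-specified estimate in this trial's own analysis.

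**Conclusion.** The point holds as a gap in estimation, and a cheap one to close. The plan collects systolic pressure repeatedly and reports no difference in mmHg for a risk it lists first. An adjusted mean would give that difference with a standard error of about 3-6 mmHg, and more power than the composite in every scenario tried (25-57% against 6-15% at 8 mmHg; 71-99% against 28-50% at 16 mmHg).

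Those ranges depend on assumed means, SDs, number of readings and treatment rule. The direction was stable; the size of the gain was not, and it fell to about 12 points when the pre-infusion reading was noisier. That case is realistic, because section 6.1.2 starts the drug in the operating room for patients extubated there, so the pre-infusion reading may be taken around extubation.

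No primary endpoint is affected, and the composite is a sensible clinical count. A non-significant result on it would not be a design failure in a trial of this size, but neither would it be evidence of no pressor effect.

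**What to change.** In 9.4.4, keep the composite count and add:

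*Time-weighted mean systolic pressure during the infusion, using one reading per hour for both cuff and arterial-line patients, will be compared between arms by linear regression on arm, adjusting for the last systolic pressure recorded before study medication starts. The difference in mmHg will be reported with its 95% CI, alongside the number in each arm given a new antihypertensive.*

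The hourly rule matters because cuff and arterial-line patients have very different numbers of readings. Peak pressure, if reported, should use the same hourly readings, since a peak rises with the number of readings. The averaging window should also be stated, because 9.4.2 refers to planned infusions of 8 hours under protocol version 1 and 3 hours under version 2.

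The cost is one paragraph, with no new visits or measurements: the infusion readings are already retrieved, and the pre-infusion value is in the same record. The downside is that antihypertensive treatment pulls the difference toward zero (about 5-15% under the assumed treatment rule), so the event count and the number treated must stay beside it.

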9.4.5 BASELINE DESCRIPTIVE STATISTICS

Baseline descriptive statistics will include demographic characteristics, past medical history including previous psychiatric diagnoses, preoperative use of psychoactive medications, and type of surgery planned. Descriptive statistics will be stratified by randomization allocation, but no inferential statistics will be used.

9.4.6 PLANNED INTERIM ANALYSES

No interim analyses are planned.

9.4.7 SUB-GROUP ANALYSES

The primary feasibility endpoints will also be assessed in sub-groups corresponding to surgical service (e.g., neurosurgery, cardiac surgery, etc.).

9.4.8 TABULATION OF INDIVIDUAL PARTICIPANT DATA

Individual participant data will not be presented.

9.4.9 EXPLORATORY ANALYSES

Exploratory analyses will include postoperative pain, intensive care unit length of stay, and hospital length of stay.

10 SUPPORTING DOCUMENTATION AND OPERATIONAL CONSIDERATIONS

10.1 REGULATORY, ETHICAL, AND STUDY OVERSIGHT CONSIDERATIONS

10.1.1 INFORMED CONSENT PROCESS

10.1.1.1 CONSENT/ASSENT AND OTHER INFORMATIONAL DOCUMENTS PROVIDED TO PARTICIPANTS

Consent forms describing in detail the study intervention, study procedures, and risks are given to the participant and written documentation of informed consent is required prior to starting intervention/administering study intervention. Written consent materials are submitted with this protocol.

10.1.1.2 CONSENT PROCEDURES AND DOCUMENTATION

Informed consent is a process that is initiated prior to the individual's agreeing to participate in the study and continues throughout the individual's study participation. Consent forms will be Institutional Review Board (IRB)-approved and the participant will be asked to read and review the document. The investigator will explain the research study to the participant and answer any questions that may arise. A verbal explanation will be provided in terms suited to the participant's comprehension of the purposes, procedures, and potential risks of the study and of their rights as research participants. Participants will have the opportunity to carefully review the written consent form and ask questions prior to signing. The participants should have the opportunity to discuss the study with their family or surrogates or think about it prior to agreeing to participate. The participant will sign the informed consent document prior to any procedures being done specifically for the study. Participants must be informed that participation is voluntary and that they may withdraw from the study at any time, without prejudice. A copy of the informed consent document will be given to the participants for their records. The informed consent process will be conducted and documented in the source document (including the date), and the form signed, before the participant undergoes any study-specific procedures. The rights and welfare of the participants will be protected by emphasizing to them that the quality of their medical care will not be adversely affected if they decline to participate in this study.

10.1.2 STUDY DISCONTINUATION AND CLOSURE

This study may be temporarily suspended or prematurely terminated if there is sufficient reasonable cause. Written notification, documenting the reason for study suspension or termination, will be provided by the suspending or terminating party to study participants, investigator, funding agency, and regulatory authorities. If the study is prematurely terminated or suspended, the Principal Investigator (PI) will promptly inform study participants, the Institutional Review Board (IRB), and sponsor and will provide the reason(s) for the termination or suspension. Study participants will be contacted, as applicable, and be informed of changes to study visit schedule.

Circumstances that may warrant termination or suspension include, but are not limited to:

- Determination of unexpected, significant, or unacceptable risk to participants
- Insufficient compliance to protocol requirements
- Data that are not sufficiently complete and/or evaluable

Study may resume once concerns about safety, protocol compliance, and data quality are addressed, and satisfy the sponsor, IRB and/or Food and Drug Administration (FDA).

